7.1.2.2. MNAR: Imputation for Deaths and Tolerability Reasons

For the primary analysis of PVR, 6MWT, and NT-proBNP efficacy endpoints, subjects who missed an assessment due to death, tolerability, or >10% change in parental prostainoid dose (including adding a new medication).will be imputed as the worst value in their planned treatment group at the specific visit.

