4.5. Standard Calculations

Variables requiring calculation will be derived using the following formulas:

- Days – A duration expressed in days between one date (*date1*) and another later date (*date2*) will be calculated using the following formulas:
 - duration in days = $date2 - date1 + 1$, where $date1 \geq$ first administration date
 - duration in days = $date2 - date1$, where $date1 <$ first administration date
- Months – A duration expressed in months is calculated as the number of days divided by 30.4375
- Weeks – A duration expressed in months is calculated as the number of days divided by 7
- Years – A duration expressed in years between one date (*date1*) and another date (*date2*) is calculated using the following formulas:
 - duration in years = $(date2 - date1 + 1)/365.25$, where $date1 \geq$ first administration date
 - duration in years = $(date2 - date1)/365.25$, where $date1 <$ first administration date
- Body Mass Index (BMI) – BMI is calculated using height (cm) and weight (kg) using the following formula:
$$BMI \text{ (kg/m}^2\text{)} = \text{weight (kg)} / ([\text{height (cm)} / 100]^2)$$
- Change (CHG) – Change will be calculated as:
$$\text{Change} = \text{later value} - \text{earlier (i.e., baseline) value}$$
- Percent change (PCHG) – Percent change will be calculated as:
$$\text{Percent change} = ([\text{Change}] / \text{earlier [i.e., baseline] value}) \times 100$$

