7.1.2.1. Missing at Random (MAR): Multiple Imputation

For the primary analysis of PVR, 6MWT, and NT-proBNP efficacy endpoints, subjects who miss an assessment for reasons other than death or other tolerability reasons, will be imputed using multiple imputation (MI) methodology based on the treatment group for time points at which no value is observed. An intercurrent event meeting will be held prior to database lock and unblinding with the medical monitor(s) and statistician(s) to review the missing efficacy assessments for each subject and determine if the missing data is MAR or missing not at random, (MNAR), i.e. informative missing.

MI will be performed under the assumption of MAR. Intermittent missing value(s) will also be replaced using MI. MI will impute 10 integer values using Markov Chain Monte Carlo (MCMC) methods assuming nonmonotone missing, a seed of 100201, 500 burn-in iterations, 100 iterations between imputations, and a non-informative prior. The imputation models based on treatment group will include randomization stratification factors, baseline WHO FC, baseline 6MWD, and baseline value of the endpoint and all previous values of the endpoint at each time point. Other baseline characteristics that may be explored will be documented in the CSR. It is anticipated that the imputation model will converge but should it not do so terms will be removed from the model to achieve convergence. The effects of any such model adjustment will be investigated.

Change from baseline to each post-baseline visit will be calculated based on observed and imputed data. Results from the analysis of each of the 10 imputed datasets will be combined using PROC MIANALYZE (Rubin's imputation rules, [Rubin 1987](#)).

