7.2. Primary Efficacy Analysis

The primary efficacy analysis will test the following hypothesis:

- H_0 : The mean change from baseline in PVR at Week 24 is equal between placebo and rodatristat ethyl.
- H_1 : The mean change from baseline in PVR at Week 24 is different between placebo and rodatristat ethyl.

In cases of missing data occurring at Week 24, missing data handling rules are specified in [Section 7.1.2](#).

Percent change from baseline in PVR at Week 24 will be analyzed using an analysis of covariance (ANCOVA) model with terms of treatment, randomization strata and baseline PVR. Estimates of least-square (LS) means, standard errors (StdErr), and 95% CIs will be presented by treatment group. In addition, the LS mean difference comparisons between each active dose and placebo, the StdErr of the difference, and 95% CI of the difference will be presented.

In order to control the Type 1 error rate, the comparisons between each active arm and the placebo arm will be tested using the Hochberg approach, where the two p-values (600 mg vs placebo and 300 mg vs placebo) will be ordered largest to smallest as $p(1) > p(2)$.

1. If $p(1) < 0.05$ then reject both null hypotheses.
2. If $p(1) > 0.05$, but $p(2) < 0.025$, then reject the null hypothesis associated with $p(2)$.

Assumptions for the ANCOVA will be checked, and if not satisfied, parametric analyses will be corroborated with appropriate nonparametric analyses, such as the Wilcoxon rank sum test stratified by randomization strata. The Hodges-Lehmann estimation of location shift and confidence interval will be produced. If the model residuals are not normally distributed, ANCOVA analysis based on ranked data will be performed.

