7.2.1. Additional Analyses of the Primary Endpoint

The rodatristat ethyl treatment groups will also be pooled and compared to placebo.

In addition to the primary endpoint, PVR values, change from baseline, and percent change from baseline to all visits will be analyzed in the same manner described above.

Summaries will be provided for the subgroups as specified in [Section 7.1.7](#) for the ITT Population. A forest plot of the LS differences and 95% CIs will be presented for Placebo versus Rodatristat ethyl 300 mg BID and Placebo versus Rodatristat ethyl 600 mg BID for the ITT and Treatment Completer populations.

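### SAP 7.1.2.2 names no scale for its worst-value imputation; on the more natural raw-PVR reading, the same event gets a percent change that depends on baseline PVR

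*SAP*

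**What the plan says.** SAP 7.1.2.2 applies to PVR, 6MWT and NT-proBNP. An assessment missed because of death, tolerability or a change of more than 10% in parenteral prostanoid dose "will be imputed as the worst value in their planned treatment group at the specific visit". No scale is given. Section 11 speaks only of the worst observation, and 7.2 refers back to 7.1.2.

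The primary analysis itself has a scale: "Percent change from baseline in PVR at Week 24 will be analyzed using an analysis of covariance (ANCOVA) model". SAP 4.5 introduces the formula with "Percent change will be calculated as" and then divides the change by the baseline value and multiplies by 100. The hypotheses in 7.2, however, are worded as mean change.

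Other text bears on which scale is meant:
- SAP 7.1.2.1: "Change from baseline to each post-baseline visit will be calculated based on observed and imputed data". The same section puts the baseline value of the endpoint into the imputation model.
- SAP 7.2.1: "PVR values, change from baseline, and percent change from baseline to all visits will be analyzed in the same manner described above".
- SAP Table 1 defines the PVR endpoint as percent change from baseline to 24 weeks, and 7.1.2.2 describes its targets as efficacy endpoints.

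On failed ANCOVA assumptions, 7.2 says: "if not satisfied, parametric analyses will be corroborated with appropriate nonparametric analyses". It adds "The Hodges-Lehmann estimation of location shift and confidence interval will be produced" and "If the model residuals are not normally distributed, ANCOVA analysis based on ranked data will be performed".

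**The concern.** Two programmers could follow 7.1.2.2 faithfully and produce different primary results. The raw reading is the more natural one: change is calculated after imputation, an endpoint that has a baseline value is a measured quantity, and PVR values are listed apart from change and percent change.

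On that reading every such patient in an arm receives the same raw PVR, which is then divided by that patient's own baseline. A low-baseline patient becomes an extreme outlier, and a high-baseline patient who dies can score no change or an improvement. The linear baseline term in the ANCOVA cannot remove a 1/b dependence. The LS-mean difference and its 95% CI are the reported primary result, and with 30 per arm one such patient can distort both. NT-proBNP has the same gap and is also analysed parametrically (7.3.3). 6MWD is less exposed because its main test uses ranks (7.3.2).

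**Working it through.** **The plan's own figure.** SAP 3 gives 30 per arm, SD 24, difference 18, two-sided 0.05 and at least 80% power. The noncentrality is (18/24) x sqrt(30/2) = 2.905. Power is 82.8% by the normal approximation and 81.5% by the noncentral t with 58 df, so the stated figure reproduces.

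**Algebra of the raw reading.** Imputed percent change = 100 x (W - b)/b = 100 x (W/b - 1). Protocol 5.1 admits b from 350 dyne·sec/cm5 with no upper limit. W is not in the documents; two assumed values show the pattern:

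| Baseline b | W = 1,400 | W = 1,500 |
|---|---|---|
| 350 | +300% | +329% |
| 700 | +100% | +114% |
| 1,400 | 0% | +7% |
| 1,500 | -7% | 0% |

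If worst is taken on the percent-change scale, every such patient in an arm gets the same score.

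**Effect on the ANCOVA (simulation).** Assumed: three arms of 30, true effects 0, 0 and -18, SD 24; baseline log-normal with median parameter 650, log-SD 0.35-0.50, floor 350; ANCOVA with baseline PVR, strata omitted; 2,000 trials per scenario. Ranges run over the log-SD.

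| Scenario | None imputed | Raw PVR | Percent change |
|---|---|---|---|
| Missingness unrelated to baseline, one per arm: CI half-width | about 12.3 | 19-25 | 13.0 |
| Same, one in active arm only: LS-mean difference | -18 | about -14 to -12 | -16.3 |
| Imputed from top third of baseline, one per arm: CI half-width | about 12.3 | 13.8-15.3 | not listed |
| Same, one in active arm only: LS-mean difference | -18 | -16.1 to -15.3 | -16.5 |

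With missingness unrelated to baseline, the median imputed change is +111% to +169% on the raw reading, against about +43% on percent change. About 3% of imputed patients score no change or an improvement (about 5% when only the active arm has one). From the top third of baseline that share is 10-14%.

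**Cross-check by formula.** A two-arm run (baseline median 700, log-SD 0.45, one imputed per arm) gave residual SDs of 23.8 with none imputed, 45.7 raw and 25.1 on percent change. Half-width is approximately t(57 df) x sqrt(2/30) x SD = 2.00 x 0.258 x SD, which gives 12.3, 23.6 and 13.0. These agree with the table.

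**The safeguards, missingness unrelated to baseline:**
- Hodges-Lehmann (unstratified): half-width 13.6-13.7 raw against 13.4-13.5 on percent change with one per arm. The estimate is -16.8 to -16.6 against -16.7 to -16.5 with one in the active arm only.
- Rank ANCOVA, one per arm: power 0.755-0.759 raw against 0.765.
- Observed-case ANCOVA, one in the active arm: about -18, half-width 12.5.
- Shapiro-Wilk at 0.05 (an assumption; the SAP names no test), one in the active arm: residuals fail in 56-73% of trials. The raw-reading LS mean averages -12.0 to -10.0 in those trials. In the rest it averages -16.5 to -16.0, close to the -16.8 to -16.3 on percent change in the same trials.

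**The case against.** The strongest reply is textual. Rule 7.1.2.2 imputes efficacy endpoints, and Table 1 defines the PVR endpoint as percent change. Read that way, the worst value is the worst percent change and nothing is wrong. The sentence in 7.1.2.1 about calculating change sits in the missing-at-random subsection, and the formulas in 4.5 are neutral on scale. This stands as far as it goes: the raw reading is more natural but not proven. It does not close the gap, because the primary result should not depend on which reading a programmer takes.

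Second, the SAP has real safeguards. SAP 7.2 adds a Hodges-Lehmann estimate and a rank ANCOVA when assumptions fail. SAP 7.1.2.4 requires observed-case and Treatment Completer analyses unconditionally; Table 8 bars imputation in the completer analyses and says substantial differences in conclusions will be investigated. An outlier artefact would therefore be visible. But these analyses corroborate or test the primary estimate and do not replace it. The observed-case and completer analyses also leave the imputed patients out, so they cannot say which scale is right.

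Third, few patients may be affected. Protocol 8.2.1 asks patients who stop treatment to keep attending visits and seeks an RHC at early stopping after at least 12 weeks. SAP Table 4 accepts any RHC from Day 2 to Day 197 as Week 24. If those imputed are mainly deaths at high baseline PVR, the shift is small. All of this stands and limits the point.

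Finally, how heavily to penalise a death is partly a matter of judgement. That is fair, but a penalty that varies with baseline PVR from +300% to below zero is not a deliberate choice of severity.

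**Conclusion.** The point holds as a gap in specification with a potentially material effect on the primary estimate, and it should be fixed. The missing scale is a matter of text. The baseline dependence on the raw reading is exact arithmetic within an arm. The sizes (half-width 19-25 instead of 13.0; LS-mean difference about -14 to -12 instead of -16.3, from one patient) rest on an assumed baseline distribution, an assumed number of imputed patients, and missingness unrelated to baseline. With high-baseline patients the shift in the LS-mean difference relative to the percent-change rule is only about 0.4 to 1.2 points.

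A reader might infer three stronger things that the documents do not support:
- That the SAP prescribes raw PVR. It prescribes no scale, and Table 1 allows percent change.
- That the trial loses its power. Simulated ANCOVA power does fall on the raw reading (0.81-0.82 to 0.33-0.51 with one imputed per arm, missingness unrelated to baseline). But the documents give no count of such patients, and the count could be zero.
- That deaths would generally be rewarded. In these runs no change or improvement is the exception (about 3-5%, or 10-14% from the top third of baseline); the usual result is an oversized worsening.

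**What to change.** In SAP 7.1.2.2, state that the worst value is taken on the scale on which each endpoint is analysed, among observed data in the planned arm at that visit:
- **PVR:** the worst observed percent change from baseline. The PVR value and absolute change are derived from it and the subject's own baseline, because 7.2.1 analyses those too.
- **NT-proBNP:** the worst observed change from baseline, as used in the 7.3.3 model. State that the supportive percent change (7.3.3.1) will then vary with baseline.
- **6MWD:** the worst observed change from baseline, as used in the 7.3.2 rank test, with any derived distance floored at 0 m. Protocol 5.1 admits 100 m, so an assumed worst change of -150 m on a 120 m baseline would otherwise give -30 m. Using the shortest raw distance instead would keep the defect: with an assumed baseline mean of 380 m, SD 90 and change SD 40-60, 2-3% of imputed patients would score a gain, or 5-8% if drawn from the lowest third.

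The cost is a few lines of SAP text and programming. The main downside is a smaller average penalty for death in PVR, about +43% at the median instead of +111% to +169%. The derived absolute PVR change will also still vary with baseline: 0.43 x 350 is about +150, and 0.43 x 1,500 is +645. Fix the scale before unblinding. If that has passed, state in the CSR which scale was used and show the primary result on the other.

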3. SAMPLE SIZE JUSTIFICATION

The sample size for this study was not based on a formal hypothesis testing. It is expected that 30 evaluable subjects per arm will provide sufficient data to assess safety and efficacy. Power calculations were conducted to examine the probability of detecting a difference among treatment groups for the percentage change of PVR from baseline.

A sample size of 90 subjects with 30 subjects to be randomized into 1 of the 3 treatment arms in a 1:1:1 randomization is planned. A sample size of 30 subjects per arm will provide at least 80% power at a significance level of 0.05 (2-sided hypothesis) to detect a treatment difference of 0.75 times of standard deviation (SD) in the percentage change from baseline of PVR from baseline between an active arm and the placebo arm. If the SD for PVR percent change is 24%, the study has 80% power to detect a difference of 18% between an active arm and the placebo arm.

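### The penalty for death, intolerance or prostanoid change is taken from the patient's own arm, so an identical event is on average scored better in the better arm, and no planned sensitivity analysis tests this

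*SAP*

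**What the plan says.** SAP 7.1.2.2 opens with its scope: "For the primary analysis of PVR, 6MWT, and NT-proBNP efficacy endpoints". It then covers "subjects who missed an assessment due to death, tolerability, or >10% change in" parenteral prostanoid dose, and such values are "imputed as the worst value in their planned treatment group at the specific visit".

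The rule enters the primary result directly. SAP 7 puts the primary efficacy analyses on the ITT population. SAP 7.2, which specifies the ANCOVA of percent change in PVR, says: "In cases of missing data occurring at Week 24, missing data handling rules are specified in" Section 7.1.2.

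SAP 11 records the move from LOCF to this approach, but calls it only a worst-observation rule. It does not name the arm or give a reason for using the patient's own. SAP 7.1.2.4 lists two sensitivity analyses for missing data: observed cases and the Treatment Completer population.

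**The concern.** The rule is meant to give a bad score to patients whose outcome is missing for a bad reason. A score of that kind should depend on the event, not on the arm in which it happened. Here the reference is the extreme of the patient's own arm. If treatment moves that arm's distribution by some amount, its expected worst value moves by the same amount. Penalised patients then reproduce the treatment difference seen in the measured patients, although they have no measurement.

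What is at stake is the primary LS mean difference, and to some degree the NT-proBNP and 6MWD results. For 6MWD the aligned rank test makes the size of the penalty matter less. The pooled active comparison in SAP 7.2.1 would also mix 300 mg and 600 mg patients scored on different penalties.

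Neither planned sensitivity analysis would show the effect. Both leave out the penalised patients, so neither says anything about the choice of reference arm.

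**Working it through.** **Inputs from the documents.** SAP 3: 30 per arm, 1:1:1, two-sided 0.05, effect 0.75 SD, and "If the SD for PVR percent change is 24%, the study has 80% power to detect a difference of 18" percent.

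**Assumptions.** The documents give no rate of death, intolerance or prostanoid change, so 2, 3 and 6 imputed of 30 are illustrative. Percent change is taken as normal with SD 24 and placebo mean 0. The worst value is taken among observed values on the percent-change scale. One dose is compared with placebo by t-test, without covariates or the Hochberg step. For the three-arm maximum, both active arms are given the same effect.

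**1. The plan's own figure.** The noncentrality is 0.75 × √(30/2) = 2.90. Power is 81.5% from the noncentral t with 58 df, and 82.8% from the normal approximation. The stated 80% is reproduced.

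**2. Size of the penalty, 3 of 30 imputed.** The maximum of 27 standard normal values has mean 2.00 and SD 0.50. Multiplied by 24, that is 48 points above the arm mean, with SD about 12.
- Placebo: 0 + 48 = +48.
- Active: -18 + 48 = +30.

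The gap is 18 points, the whole assumed effect. In simulation the active arm has the lower maximum in about 86% of trials.

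**3. Effect on the estimate, equal counts.**
- Own-arm rule, 3 v 3: (27/30)(-18) + (3/30)(30 - 48) = -16.2 - 1.8 = -18.0.
- Common penalty, 3 v 3: (27/30)(-18) + 0 = -16.2.
- Common penalty, 6 v 6: (24/30)(-18) + 0 = -14.4. The own-arm rule again gives -18.0.

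**4. Unequal counts, 6 active v 2 placebo.** Under a common penalty of about +50 the difference is (24/30)(-18) + (6/30 - 2/30)(50) = -14.4 + 6.7 = -7.7. The own-arm rule gives -11.8 in simulation.

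**5. Simulated estimate and power at a true effect of -18.** The common penalty is the worst observed value over all three arms.

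| Imputed, active v placebo | Own arm: estimate, power | Common: estimate, power |
|---|---|---|
| 2 v 2 | -18.0, 75% | -16.8, 66% |
| 3 v 3 | -18.0, 72% | -16.2, 58% |
| 6 v 6 | -18.0, 66% | -14.4, about 35% |
| 6 v 2 | -11.8, 38% | -7.7, 7% |

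**6. No true effect.** With equal counts the own-arm penalties have the same mean and each one-sided rejection rate is 2.0% to 2.7%, against a nominal 2.5%. With 6 active v 2 placebo events the own-arm rule gives +6.1 points against the drug. Under the common penalty with equal counts, total two-sided rejection falls to 1.3% (3 v 3) and 0.4% (6 v 6).

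**The case against.** The strongest reply is that the own-arm rule is not lenient. A penalised active patient still gets the worst result in the arm, about 2 SD above that arm's mean. The alternative costs real power in a trial sized for 80%, and it still draws its value from one extreme patient, now one in the whole trial. All of that stands.

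A reader might infer three stronger things that the documents do not support.

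- *The rule manufactures a drug effect.* It does not: with no true effect and equal event rates there is no material inflation. If the drug raised PVR by 18 points, the gap would reverse and active events would score 18 points worse.
- *Deaths on drug never count against it.* They do when they are in excess: 6 v 2 moves the own-arm estimate from -18 to -11.8. The credit is only relative to the same event on placebo.
- *The active arm always gets the milder score.* The penalty follows the arm's worst value, not its mean. At the planned effect the order reverses in about 14% of simulated trials.

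The sizes are also open to challenge. The SAP does not say whether the worst value is raw PVR or percent change. SAP 7.1.2.1, on multiple imputation, derives change from observed and imputed data, which points towards raw PVR, and no baseline spread is given to convert the figures. Missing PVR is also limited by the early-termination RHC after at least 12 weeks of treatment (Protocol 8.2.1) and by the Day 2 to 197 window for the Week 24 RHC (SAP Table 4). Six of 30 is therefore a stress case, not a forecast. Earlier losses will usually leave no post-baseline PVR, however, so the rule can apply.

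**Conclusion.** The point holds in a limited form. When the drug works, the own-arm reference makes an identical event score better on average in the better arm, by about the size of the drug effect. The estimate is then larger than under a common penalty by 1.2 points with 2 imputed per arm, 1.8 with 3, 3.6 with 6, and about 4.1 with 6 active v 2 placebo.

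The average direction follows from the rule itself. The sizes rest on assumed event counts, normality and the percent-change scale. This is a weakness in how informative missingness is scored, and one the planned sensitivity analyses cannot reveal. It is not a type I error problem.

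**What to change.** In SAP 7.1.2.2, replace the reference to the worst value in the planned treatment group with: *the worst observed value at that visit across all three treatment groups*. State at the same time whether this is taken on raw PVR or on percent change. If the primary rule is kept, add the common penalty to SAP 7.1.2.4 as a pre-specified sensitivity analysis and report both results.

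The change needs a few words and no new data, but it is not free. The estimated effect is smaller, and power falls from about 75% to 66% with 2 imputed per arm and from 72% to 58% with 3. The test becomes conservative under the null, and the penalty still rests on one extreme patient. If that power loss is not acceptable for the primary analysis, the sensitivity-analysis route makes the dependence visible without it.
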